## **1. OBJECTIVES**

### **1.1 Study Design**

This is a single-arm, Phase II study of the FOLFIRINOX regimen in combination with the angiotensin II type I receptor blocker Losartan, followed by restaging and radiation therapy with capecitabine, in the treatment of patients with locally advanced unresectable pancreatic adenocarcinoma.

### **1.2 Primary Objective**

- 1.2.1 To determine the rate of R01 resection in patients with locally advanced unresectable pancreas cancer treated with the combination of FOLFIRINOX-Losartan followed by restaging and radiation therapy with capecitabine.

### **1.3 Secondary Objectives**

- 1.3.1 To determine the progression-free survival of patients with locally advanced disease who receive FOLFIRINOX-Losartan and radiation therapy.
- 1.3.2 To determine overall survival in patients treated with FOLFIRINOX-Losartan and radiation therapy.
- 1.3.3 To determine the overall survival of patients with locally advanced disease who receive FOLFIRINOX-Losartan without radiation (i.e. patients who demonstrate progression at restaging.)
- 1.3.4 To determine the toxicity of FOLFIRINOX – Losartan in patients with locally advanced pancreatic cancer.
- 1.3.5 To determine the toxicity of FOLFIRINOX – Losartan and radiation in patients with locally advanced pancreatic cancer.

- 1.3.6 To determine the rate of downstaging to surgical resection of FOLFIRINOX-Losartan followed by radiation in patients with locally advanced pancreatic cancer.
- 1.3.7 To determine the correlation between a panel of somatic genetic mutations (SNaPSHOT) and outcome in locally advanced pancreatic cancer treated with FOLFIRINOX-Losartan +/- radiation/capecitabine.
- 1.3.8 To determine the correlation between circulating biomarkers of TGF- $\beta$ 1 downregulation, including circulating Collagen I levels, and outcome in locally advanced pancreatic cancer treated with FOLFIRINOX-Losartan +/- radiation/capecitabine.
- 1.3.9 To describe quality of life, symptom burden and mood in the study population.
- 1.3.10 To measure utilization of health services (emergency room, hospital and intensive care unit, palliative care) in the study population.

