#### 10.1.2 Progression-free survival

Progression-free survival will be defined as the time from the start date of protocol therapy to first objective documentation of progressive disease (distant or local) or death. Patients who die without a reported prior progression will be considered to have progressed on the day of their death.

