#### 10.1.3 Time to death

Time to death will be calculated as the time from the start date of protocol therapy to date of death

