## 14 STATISTICAL CONSIDERATIONS

### 14.1 Study Design

14.2 **The single-arm protocol is a phase II study to investigate combining Losartan with FOLFIRINOX for induction chemotherapy followed by restaging and radiation therapy with capecitabine in the treatment of patients with locally advanced pancreatic cancer. The primary endpoint is the rate of R0 (negative margin) resection determined by final pathology of the surgical specimen. Our historical data show a <10% rate of R0 resection among unresectable patients treated with induction chemotherapy followed by chemoradiation. The protocol will have demonstrated an improvement in efficacy if R0 resection were achieved in at least 9 of 50 patients. The decision rule is associated with 91% power if FOLFIRINOX-Losartan with short-course radiation and capecitabine were to improve the R0 resection rate to 25%. In contrast, the probability of a type 1 error is only 6% if the underlying rate of R0 resection were truly the same as the historical level of 10%. All protocol patients who start induction chemotherapy will be included in the denominator for R0 resection analysis, including those who do not undergo surgery due to early progression or other reasons. Sample Size/Accrual Rate** The accrual goal of 50 patients is projected to be enrolled over a total period of 4.5 years. The estimate is based on the overall rate of accrual based on the first 32 patients since the protocol was first open to patient entry. Therefore, we project the enrollment of the remaining 18 patients will require no more than 1.5 years.

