### 14.3 Analysis of Secondary Endpoints

- 14.3.1 **Progression-free survival:** All patients who start induction chemotherapy will be analyzed based on the definition in Section 10.1.2. The progression-free survival duration of patients who are alive and progression will be censored at their date of last follow-up. The Kaplan-Meier method will be used to estimate progression-free survival with 90% confidence intervals constructed by Greenwood's formula.
- 14.3.2 **Overall survival:** Overall survival will be defined as the duration between the start date of protocol therapy and death. The survival time of patients who are not known to have died will be censored at the date they are last known to be alive. The Kaplan-Meier method will be used to estimate overall survival estimation with 90% confidence intervals constructed by Greenwood's formula.
- 14.3.3 **Toxicities:** All patients who begin induction chemotherapy will be included in the toxicity profile of Losartan combined with induction FOLFIRINOX. Summaries of toxicities will include the frequency and proportion of patients experiencing each toxicity, as well as summaries by toxicity category and toxicity grade. We shall report separately the additional treatment-related toxicity following radiation in patients who do not have progressive disease at the restaging interval after induction chemotherapy.
- 14.3.4 **Downstaging:** A fraction of patients may proceed to surgical resection following the conclusion of protocol therapy if the tumor shrinkage were sufficient to be considered resectable. The rate of downstaging to surgical resection will be determined as the proportion of initially unresectable patients who eventually undergo pancreaticoduodenectomy or distal pancreatectomy. The pathologic downstaging rate will be calculated as the proportion of resected patients with the primary tumor and nodes downstaged based on final pathology of the surgical specimen.
- 14.3.5 **Correlation of biomarkers with outcome:** Correlative studies will be conducted to characterize circulating collagen and angiogenesis biomarkers (8.1.1), as well as somatic genetic mutations characterized by the SNaPshot platform (8.1.2). Due to the modest patient numbers, analysis will be limited generally to two-group comparisons of each

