### **4.3 Reporting and Exclusions**

All patients who begin protocol treatment will be included in the primary and the relevant secondary endpoints.

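### Objective 1.3.3 equates no radiation with progression at restaging and has no line in 14.3; survival follow-up is unclear for patients removed without progression

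*Combined protocol and SAP*

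**What the plan says.** Objective 1.3.3 seeks the "overall survival of patients with locally advanced disease who receive FOLFIRINOX-Losartan without radiation (i.e. patients who demonstrate progression at restaging"); the parenthesis closes there. Objectives 1.3.1 and 1.3.2 concern patients who receive both components; 1.3.1 reads "To determine the progression-free survival of patients with locally advanced disease who receive FOLFIRINOX-Losartan and radiation therapy".

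The analysis sections use one population and one clock:

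- **PFS, 14.3.1:** "All patients who start induction chemotherapy will be analyzed based on the definition in Section 10.1.2". Section 10.1.2 starts that clock at the start of protocol therapy.
- **OS, 14.3.2:** "Overall survival will be defined as the duration between the start date of protocol therapy and death". Section 10.1.3 agrees: "Time to death will be calculated as the time from the start date of protocol therapy to date of death". Neither names a population. Reporting and Exclusions (numbered 4.3, at the end of section 14) supplies it: "All patients who begin protocol treatment will be included in the primary and the relevant secondary endpoints".
- **Split by radiation:** 14.3.3 reports toxicity after radiation separately. Survival has no such split.

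On follow-up, section 5.6 first says that patients are followed to progression and then for survival. It then says that those removed for unacceptable adverse events are followed until the event resolves or stabilizes. Section 5.7 removes participants when any 5.5 criterion applies, then exempts progressors, who stay on for survival follow-up. Sections 6.2.2.1 (hypotension) and 6.2.2.2 (hyperkalemia) un-enrol certain patients and do not mention follow-up.

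**The concern.** There are two linked problems.

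First, the main clause of 1.3.3 covers everyone who misses radiation, while its parenthesis covers only restaging progressors. Two analysts could report different cohorts and both claim to follow the plan. Whichever cohort is used, the group is defined by something seen at restaging, but the only clock on offer starts at the first dose. Everyone in the progressor group must have lived to the scan, so the time before it is counted as survival that could not have ended in death.

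Second, a patient who leaves for toxicity, illness or un-enrolment may have no survival status collected after removal. Such patients would be censored in the all-starter OS curve for a reason probably related to prognosis. Kaplan-Meier estimation assumes that it is unrelated.

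**Working it through.** **Plan's own figures.** No sample size, power or precision is stated for PFS or OS, so there is no figure on this point to reproduce. The primary rule (at least 9 of 50) does reproduce by exact binomial: power 0.908 at 25% (stated 91%) and type I error 0.058 at 10% (stated 6%). Nothing below touches it.

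**Step 1. Does no radiation mean progression?** Under 5.1, patients without progression on either restaging scan go on to radiation. That intended pathway is what the parenthesis describes. The other exits are:

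| Route to no radiation without progression at restaging | Section |
|---|---|
| Intercurrent illness, unacceptable adverse event, withdrawal, change in condition | 5.5 |
| Un-enrolment for persistent hypotension | 6.2.2.1 |
| Un-enrolment for recurrent hyperkalemia | 6.2.2.2 |
| Death before induction ends | foreseen in 10.2.2 |

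The main clause of 1.3.3 includes these patients and its parenthesis excludes them.

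**Step 2. Survival credited before the scan.** Inputs: 14-day cycles with a +3/-1 day window (5.1, 6.2.2); scans after cycles 4 and 8, with up to one week's delay between cycles for restaging (5.1); scans allowed after pump disconnect in cycles 4 and 8 (section 9, note 5), taken as 2 days after Day 1 because the infusion runs 46-48 hours. Days are counted from Cycle 1 Day 1, with 30.44 days per month.

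| Scan | Earliest, 14-day cycles | Latest, nominal | Earliest, 13-day cycles |
|---|---|---|---|
| Interim | 3×14 + 2 = 44 (1.4 months) | 4×14 + 7 = 63 (2.1 months) | 3×13 + 2 = 41 |
| Final | 7×14 + 2 = 100 (3.3 months) | 8×14 = 112 (3.7 months) | 7×13 + 2 = 93 |

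Longer cycles or toxicity holds push the scans later. For each progressor, survival from start of therapy equals this interval plus survival from the scan, so the clock alone lengthens the reported figure by that amount.

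**Step 3. Follow-up passages side by side.** The opening sentence of 5.6 can be read as covering every patient. Its adverse-event sentence names an end point and does not mention survival. Section 5.7 removes patients for any 5.5 criterion and promises survival follow-up only to progressors. Read together, they leave it open whether a patient removed without progression is followed to death.

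**Step 4. Possible effect on all-starter OS (illustration only; every input is assumed).** Take exponential times with median PFS 6 months and median post-progression survival 6 months. Let 4 or 8 of 50 patients be removed progression-free in the first 3.5 months, with follow-up ending one month later. About 4 or 8 deaths then go unseen.

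- If removal is unrelated to prognosis, median OS moves by about 0.2 month or less.
- If removed patients then die at 1.5-2 times the rate, the median reads 14.4 against a true 13.7-14.0 months (4 removed), or 14.3 against 13.0-13.6 (8 removed). It is too high by about 0.4-1.3 months.

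**The case against.** The strongest reply is that the plan is less incomplete than it looks. OS is defined once, with no exception, so a default origin exists. The parenthesis in 1.3.3 names an intended group that matches 5.1. The adverse-event sentence in 5.6 contains no word limiting follow-up to that event and can be read as an added duty. Section 12.1.2 lists a follow-up/survival form. All of this stands. The plan does not lack every element; its elements do not fit together.

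Stronger readings are tempting but not supported:

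- **That 1.3.1 and 1.3.2 have no valid analysis.** A reader might infer this from their wording. Section 14.3.1 and Reporting and Exclusions answer them in all starters, which is sound for a regimen that includes induction. The primary endpoint is handled the same way: "All protocol patients who start induction chemotherapy will be included in the denominator for R0 resection analysis".
- **That irradiated-only survival will be inflated.** Radiation nominally starts 7×14 + 15 = 113 to 7×14 + 43 = 141 days after Cycle 1 Day 1, or 7×13 + 15 = 106 to 7×17 + 43 = 162 days across the cycle window. A PFS clock started at first dose would include that time. No irradiated-only survival analysis is planned in 14.3, so this is a caution for any later report and not a flaw in a stated analysis.
- **That the protocol stops survival follow-up after removal for toxicity.** The text is ambiguous. Lost deaths are a conditional risk.

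**Conclusion.** The point holds, as a gap in descriptive secondary estimates. Objective 1.3.3 has no line in 14.3, its parenthesis is contradicted by the protocol's own exits, and the common origin credits restaging progressors with nominally 44-63 or 100-112 days of survival before the scan (from day 41 or day 93 with 13-day cycles). These ranges follow from the schedule and are not guaranteed minima.

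The follow-up conflict matters more widely because it reaches the all-starter OS curve. Its size cannot be taken from the documents: it depends on how many patients leave without progression, whether their survival is then sought, and how their prognosis differs. The 0.4-1.3 months above rests wholly on assumed values and should not be quoted as an expected bias.

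No between-group test is planned and the primary R0 endpoint is unaffected. The change should be made before analysis, so that cohort and clock are not chosen with the data in hand.

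**What to change.** 1. **Follow-up.** Reconcile 5.6, 5.7, 6.2.2.1 and 6.2.2.2 so that survival status is collected for every patient who starts therapy, whatever the reason for removal, subject to consent. This concerns data collection only; it changes no treatment or un-enrolment rule.
2. **Objective 1.3.3.** Add a line to 14.3.2 that defines the group as patients with progression at restaging and reports their survival from the date of the scan showing progression. Label it survival after restaging progression, so that the OS definition stands. Tabulate separately, by reason, the patients who miss radiation without restaging progression, including any who die before restaging. Align the wording of 1.3.3.
3. **Interpretation.** State that these post-baseline groups are descriptive, that they differ by selection, and that no radiation effect will be inferred from them. If irradiated-only PFS or OS is ever reported, time it from the start of radiation.
4. **Objectives 1.3.1 and 1.3.2.** Add only a note that they are answered in all starters.

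**Cost.** Wording and one small descriptive analysis. Section 5.7 already requires the reason and date of removal on the case report form, and 12.1.2 already lists staging, chemoradiation, off-study and survival forms. Survival status must be sought for a few more patients, and the progressor survival figure becomes shorter by the interval to the scan.

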## **2 BACKGROUND**

### **2.1 Study Agents**

#### **2.1.1 5-Fluorouracil**

5-Fluorouracil (5-FU) is a pyrimidine antagonist that interferes with nucleic acid biosynthesis. The deoxyribonucleotide of the drug inhibits thymidylate synthetase, thus inhibiting the formation of thymidylic acid from deoxyuridylic acid, thus interfering in the synthesis of DNA. It also interferes with RNA synthesis. It is systemically metabolized, with the enzyme dihydropyrimidine dehydrogenase (DPD) being rate-limiting. It forms the backbone of treatment for most gastrointestinal malignancies, and is a crucial component of the FOLFIRINOX regimen, in which it is administered as a 400 mg/m^2 bolus, followed by a 2400 mg/m^2 46-48 hour infusion. Neutropenia and diarrhea are the dose limiting toxicities of 5-fluorouracil. Nausea and vomiting with 5-fluorouracil tends to be mild but patients often become dehydrated due to diarrhea. Stomatitis is a common complication of 5-fluorouracil and typically occurs 5-8 days after initiating treatment. Ileus may occur as a result of 5-fluorouracil enteritis. Anemia and thrombocytopenia are also associated complications. Dermatologic side effects are common, and

include dryness of skin, palmar-plantar erythrodysesthesias (Hand-Foot syndrome), alopecia, loss of nails/brittle nails and a maculopapular rash. Neurological complications are rare and consist of ataxia. Cardiotoxicity is another very rare complication of 5-fluorouracil, manifested as ischemia and sometimes asymptomatic S-T changes. Excessive lacrimation is common and less common is eye duct stenosis. 5-FU may also increase the INR in patients taking warfarin.

### 2.1.2 Oxaliplatin

Oxaliplatin is a platinum compound classified with the alkylating agents. Its mechanism of action is via intra-strand cross-linking, thereby inhibiting DNA replication and transcription. In the FOLFIRINOX regimen it is administered as an 85 mg/m^2 infusion over 2 hours.

Neurotoxicity is generally the dose-limiting toxicity of the drug, as it causes both immediate and delayed neuropathy manifesting as cold sensitivity (immediate) and paresthesias, numbness, and ataxia (incoordination, including abnormal gait) (delayed.) It is also associated with CNS complaints such as insomnia, mood alteration (depression, anxiety) neuropathy cranial (ptosis), vertigo, neuropathy sensory (including acute laryngo-pharyngeal dysesthesias, L'Hermitte's sign, paresthesia). Oxaliplatin is associated with allergic and hypersensitivity reactions including chills, flushing, or anaphylaxis. It is associated with mild ototoxicity. Bone marrow suppression (particularly thrombocytopenia), cardiac arrhythmia, and hepatic toxicity, specifically increased alkaline phosphatase, increased bilirubin, increased GGT (gamma-glutamyl-transpeptidase), hepatic enlargement, increased AST (AST) (serum glutamic oxaloacetic transaminase), increased SGPT (ALT) (serum glutamic pyruvic transaminase) have been observed. It is associated with rare but serious pulmonary fibrosis.

### 2.1.3 Irinotecan

Irinotecan is a camptothecin topoisomerase I inhibitor commonly used in gastrointestinal malignancies. In the FOLFIRINOX regimen it is delivered as a 180 mg/m^2 infusion over 90 minutes on Day 1 of treatment. Diarrhea and neutropenia are the major dose-limiting toxicities of irinotecan. Diarrhea can occur either acutely (within the first 24 hours) and delayed (after 2-4 days.) Acute diarrhea is thought to be mediated by non-competitive inhibition of acetyl cholinesterase activity by irinotecan, and is readily treatable with atropine, 0.25-1 mg, intravenously. Delayed diarrhea often manifests after the second or third weekly dose of

irinotecan, and is thought to be secretory in nature, resulting from abnormal intestinal ion transport. Anti-diarrheal agents, such as loperamide, diphenoxylateatropine (Lomotil®), octreotide, scopolamine and bismuth are typically ineffective once grade IV diarrhea has occurred. The diarrhea usually lasts 5-7 days before resolving. Early recognition of diarrhea and prompt institution of an intensive and prolonged course of loperamide appears to be the most effective approach to this problem. Myelosuppression is manifested primarily as leukopenia and neutropenia. Other toxicities include nausea, vomiting, alopecia and cumulative fatigue or asthenia. Instances of possible drug related hepatic toxicity have occurred, but are rare.

#### 2.1.4 Leucovorin

Leucovorin is a reduced folate which, when combined with 5FU, augments 5FU cytotoxicity by increasing the inhibition of TS by the 5FU active metabolite FdUMP. It is well-tolerated but can be associated with allergic reactions (rash, urticaria, anaphylaxis) and is contraindicated in patients with B12 deficiency and pernicious anemia.

#### 2.1.5 Losartan

Losartan is an angiotensin II type I receptor blocker (ARB) used in the treatment of essential hypertension and diabetic nephropathy. It is a selective competitive angiotensin II receptor antagonist that acts as an antihypertensive by blocking angiotensin II and its two major downstream pathways: direct vasoconstriction, and stimulation of aldosterone secretion. Its mechanisms of action in the cancer milieu will be discussed separately. It is administered orally and the usual starting dose in adults with hypertension is 50 mg, with doses up to 100 mg based on blood pressure response. Patients with baseline volume depletion are started on a dose of 25 mg PO daily with the dose titrated up as tolerated. There are no specific dosing adjustments for hepatic or renal impairment, but use in patients with chronic kidney disease whose calculated GFR is less than 30mL/minute/1.73m^2 is not recommended. Losartan is associated with the significant adverse reactions (>10% incidence) of chest pain, fatigue, hypoglycemia, diarrhea, urinary tract infection, anemia, weakness, back pain, and cough. Less common, but important, adverse reactions include hypotension, orthostatic hypotension, dizziness, hyperkalemia,

gastritis, muscle weakness, bronchitis. Rarely, losartan is associated with life-threatening angioedema, acute psychosis, and cardiac arrhythmia.

#### 2.1.6 Capecitabine

Capecitabine is a rationally designed oral fluoropyrimidine.(1, 2) Given its lack of a need for an implantable access device or portable infusion pump and patient convenience, it has become an attractive agent to be combined with radiation therapy. Capecitabine undergoes three steps of enzymatic activation before converting to the active drug. It is readily absorbed from the gastrointestinal tract. In the liver, a 60 kDa carboxyesterase hydrolyzes much of the compound to 5'-deoxy-5-fluorocytidine (5'-DFCR). Cytidine deaminase, an enzyme found in most tissues, including tumors, subsequently converts 5'-DFCR to 5'-deoxy-5-fluorouridine (5'-DFUR). The enzyme, thymidine phosphorylase (dThdPase), then hydrolyzes 5'-DFUR to the active drug 5-FU. Many tissues throughout the body express thymidine phosphorylase. Some human carcinomas express this enzyme in higher concentrations than surrounding normal tissues. Capecitabine is rapidly and extensively absorbed with the peak plasma concentrations for the drug and its two main metabolites occurring shortly (0.5 - 1.5 hours) after administration. Then concentrations decline exponentially with a half-life of 0.5 - 1 hour. Plasma concentrations of the cytotoxic moiety 5-FU are very low.

Capecitabine is generally well tolerated. Major side effects include diarrhea, nausea, hand-and-foot syndrome, vomiting, fatigue, and stomatitis. The most frequent grade 3 or 4 laboratory abnormality was elevated total bilirubin and alkaline phosphatase, or abnormal liver function tests. Myelosuppression has been rarely reported (< 2%).

Its role as a radiosensitizer has been most studied in rectal cancer. Dunst et al reported the results of a phase I study using capecitabine in T3 and T4 rectal cancer.(3) Thirty-six patients with rectal cancer received treatment in the adjuvant, neoadjuvant, or palliative setting with a total radiation dose of 50.4 Gy. Capecitabine was administered at escalating doses from 250 to 1,250 mg/m^2 twice a day concurrently with radiation. They were able to escalate the capecitabine dose to 825 mg/m^2 twice a day. Dose-limiting grade 3 hand-and-foot syndrome was observed in two of six patients treated at 1,000 mg/m^2 bid. Other toxicities were generally rare and/or mild. One pathologic complete remission of a T3N1 tumor and nine partial remissions were observed in 10 patients treated in the neoadjuvant setting. In another study,

capecitabine was administered concurrently with radiotherapy in locally advanced rectal cancer.(4) The treatment consisted of 2 cycles of 14-day oral capecitabine (825 mg/m^2 BID) and leucovorin (10 mg/m^2 BID), each of which was followed by a 7-day rest period. The overall downstaging rate, including both primary tumor and nodes, was 84%. A pathologic complete response was achieved in 31% of patients. Twenty-one patients had tumors located initially 5 cm or less from the anal verge; among the 18 treated with surgery, 72% received sphincter-preserving surgery. Grade 3 toxicities included hand-foot syndrome (7%), fatigue (4%), diarrhea (4%), and radiation dermatitis (2%). NSABP is planning a prospective randomized trial to compare capecitabine with infusional 5-FU in patients undergoing preoperative radiation therapy. Preliminary results from a trial combining capecitabine with radiation therapy in patients with locally advanced pancreatic cancer demonstrated the combination to be safe and tolerable at a dose of 825 mg/m^2 twice daily.(5)

[figure not shown]
